#### 4 **Population**

The study population consists of pediatric HF patients 1 month to < 18 years, inpatient or outpatient, with systemic left ventricle systolic dysfunction (LVEF ≤45% or a fractional shortening  $\leq 22.5\%$ ). For inclusion criteria details regarding LVEF and fractional shortening, refer to Section 4.1. The study will enroll at least 18 patients in Part 1 and 360 patients in Part 2 (Efficacy) at centers worldwide. With an expected screen failure rate of 35% for both Part 1 (PK/PD) and Part 2 (Efficacy), it is estimated that approximately 46 patients will have to be screened for Part 1 and 554 patients will have to be screened for Part 2.

For Part 1, at least 18 subjects will be divided across three groups based on age: **Group 1**: 6 to < 18 years (6 observations for the LCZ696 0.8 mg/kg dose and 6 observations for the LCZ696 3.1 mg/kg dose); Group 2: 1 to < 6 years (6 observations for the LCZ696 0.8 mg/kg dose and 6 observations for the LCZ696 3.1 mg/kg dose); **Group 3**: 1 month to < 1 year (approximately 4 observations for LCZ696 -0.4 mg/kg dose and approximately 4 observations for the LCZ696 1.6 mg/kg dose). Eligible patients will participate in the LCZ696 0.8 mg/kg and 3.1 mg/kg doses in Groups 1 and 2 and in the LCZ696 0.4 mg/kg and 1.6 mg/kg doses in Group 3. Patients who do not participate in the LCZ696 3.1 mg/kg (Group 1 or 2) or 1.6 mg/kg (Group 3) dose will be replaced. To ensure that patients are enrolled in both high and low end of the 6 to < 18 years of age group, approximately 50% patients will be enrolled who are 6 to 11 years of age in Group 1.

For Part 2, patients will be stratified by age (Age Groups 1, 2 and 3) and NYHA/Ross class group (Class I/II, Class III/IV) at randomization to ensure a balanced distribution of treatment allocation within each age group. Patients who discontinue from Part 2 will not be replaced.

## 4.1 Inclusion criteria

Patients eligible for inclusion in this study (Part 1 and Part 2) must fulfill all of the following criteria:

- 1. Written informed consent by parent(s)/legal guardian(s) for the pediatric patient must be obtained before any study-specific assessment is performed.\* A consent or assent may also be required for some patients depending upon their age and local requirement.
- 2. Male or female, inpatient or outpatient, 1 month (≥44 weeks post-conception for pre-term infants) to < 18 years of age.
- 3. Chronic heart failure resulting from left ventricular systolic dysfunction, and receiving chronic HF therapy (if not newly diagnosed)..
- 4. NYHA classification II-IV (older children: 6 to less than 18 year old) or Ross HF classification II-IV (younger children: less than 6 year old) any time prior to screening. [Note: Age Group 1 patients may be NYHA class I at time of screening if there is a prior history of NYHA class II-IV. Age Group 2 patients must be Ross class II or higher at time of randomization].
- 5. Systemic left ventricular ejection fraction (EF) ≤ 45% or fractional shortening ≤22.5% (assessed by echocardiogram, MRI, MUGA or left ventricular angiogram within 1 month before patient begins Part 2). [Note: The study will target enrollment of approximately 80% patients with a systemic left ventricular ejection fraction (EF) ≤ 40% or fractional shortening ≤20% for Part 2 only].
- 6. Biventricular physiology with systemic left ventricle.
- 7. For Part 1 PK/PD, patients must be treated with an ACEI or ARB prior to screening. For Part 1 PK/PD, patients in Group 1 and 2 must be currently treated with a daily dose equivalent of at least enalapril 0.2 mg/kg (Table 3-1) prior to the LCZ696 3.1 mg/kg single dose assessment. For Part 1 PK/PD, patients in Group 3 must be currently treated with a daily dose equivalent of at least enalapril 0.1 mg/kg (Table 3-1) prior to the LCZ696 1.6 mg/kg single dose assessment
- 8. HF etiologies include: Congenital Cardiac Malformation with systemic ventricular systolic dysfunction; Idiopathic Cardiomyopathy; Familial/Inherited and/or Genetic Cardiomyopathy; History of Myocarditis; Neuromuscular Disorder; Inborn Error of Metabolism; Mitochondrial Disorder; Acquired (Chemotherapy, Iatrogenic, Infection, Rheumatic, Nutritional); Ischemic (e.g. Kawasaki Disease, post-operative); Left ventricular noncompaction
- \*Assessments of HF (e.g. ECHO) in patients that are done according to current local institutional/hospital standard protocol or that are part of routine clinical care can be used to support patient screening and may have taken place before signing informed consent. An informed consent must be obtained from a patient once they become 18 years old during the study.

## 4.2 Exclusion criteria

Patients fulfilling any of the following criteria are not eligible for inclusion in this study (Part 1 and Part 2). No additional exclusions may be applied by the Investigator, in order to ensure that the study population will be representative of all eligible patients.

- 1. Patients with single ventricle or systemic right ventricle
- 2. Patients listed for heart transplantation as United Network for Organ Sharing (UNOS) Status 1A or hospitalized waiting for transplant while on inotropes or with ventricular assist device at time of entry into the study
- 3. Sustained or symptomatic dysrhythmias uncontrolled with drug or device therapy
- 4. For Part 2 only, patients that have had cardiovascular surgery or percutaneous intervention to palliate or correct congenital cardiovascular malformations within 3 months of the screening visit. Patients anticipated to undergo corrective heart surgery during the 12 months after entry into Part 2.
- 5. Patients with unoperated obstructive or severe regurgitant valvular (aortic, pulmonary, or tricuspid) disease, or significant systemic ventricular outflow obstruction or aortic arch obstruction
- 6. Patients with restrictive or hypertrophic cardiomyopathy
- 7. For Part 2 only, active myocarditis (diagnosed with presumed or acute myocarditis within 3 months of enrollment)
- 8. Symptomatic hypotension or blood pressures (BPs) below the calculated 5th percentile systolic BP (SBP) for age at screening visit and as described in Appendix 4
- 9. Renal vascular hypertension (including renal artery stenosis)
- 10. Severe pulmonary hypertension (defined by pulmonary vascular resistance (PVR) index >6 Wood units-m²) unresponsive to vasodilator agents (such as oxygen, nitroprusside or nitric oxide). Note measurement of PVR is not a requirement for study eligibility
- 11. History or current clinical evidence of moderate-to severe obstructive pulmonary disease or reactive airway diseases (e.g. asthma)
- 12. Serum potassium >5.3 mmol/L at Visit 1 or at Visit 301
- 13. Patients with significant renal (eGFR calculated using the modified Schwartz formula < 30% mean GFR for age, Appendix 10, Table 22-1); hepatic (serum aspartate aminotransferase or alanine aminotransferase > 3 times upper limit of normal); gastrointestinal or biliary disorders (that could impair absorption, metabolism, or excretion of orally administered medications)
- 14. Concurrent terminal illness or other severe disease (e.g. acute lymphocytic leukemia) or other significant laboratory values that, in the opinion of the Investigator, precludes study participation or survival
- 15. Patients with a history of angioedema
- 16. Patients with allergy or hypersensitivity to ACEI or ARB
- 17. Patients who have parents or legal guardians who do not give consent or allow the child to give assent, or inability of the patient or the parents/legal guardians to follow instructions or comply with follow-up procedures
- 18. Pregnant or nursing (lactating) women
- 19. Women of child-bearing potential, defined as all women physiologically capable of becoming pregnant, unless they are using highly effective methods of contraception during dosing of investigational drug and for 7 days after study drug discontinuation. Highly effective contraception methods include:

- Total abstinence (when this is in line with the preferred and usual lifestyle of the subject and if acceptable by the local regulation). Periodic abstinence (e.g. calendar, ovulation, symptothermal, post-ovulation methods) and withdrawal are not acceptable methods of contraception
- Female sterilization (have had surgical bilateral oophorectomy with or without hysterectomy), total hysterectomy or tubal ligation at least six weeks before taking investigational drug. In case of oophorectomy alone, only when the reproductive status of the woman has been confirmed by follow up hormone level assessment
- Male sterilization (at least 6 months prior to screening). For female subjects on the study, the vasectomized male partner should be the sole partner for that subject
- Use of oral, (estrogen and progesterone), injected or implanted hormonal methods of contraception or placement of an intrauterine device (IUD) or intrauterine system (IUS), or other forms of hormonal contraception that have comparable efficacy (failure rate <1%); for example hormone vaginal ring or transdermal hormone contraception
- In case of use of oral contraception women should have been stable on the same pill for a minimum of 3 months before taking investigational drug
- 20. Use of other investigational drugs within 5 half-lives or within 30 days of enrollment, whichever is shorter
- 21. History of hypersensitivity to any of the study drugs or its excipients or to drugs of similar chemical classes
- 22. Any major solid organ transplant recipient
- 23. History of malignancy of any organ system, treated or untreated, within the past year with a life expectancy less than 1 year
- 24. Any advanced severe or unstable disease that may interfere with the primary or secondary study outcome evaluations or put the patient at special risk
- 25. Any other medical conditions that may put the patient at risk or influence study results in the Investigator's opinion, or that the Investigator deems unsuitable for the study
- 26. Patient breastfed by a mother taking ACEI

#### 5 Treatment

# 5.1 Study treatment

## 5.1.1 Investigational and control drugs

The sponsor will provide the following study drugs:

# Part 1 - PK/PD treatment epoch

All eligible patients that enter Part 1 will receive LCZ696.

The LCZ696 study medication is available as granules or liquid formulation based on age, weight, dosing, and patient's ability to take study medication (Pharmacy Manual).

The following study drug will be provided:

• LCZ696 3.125 mg granules (packaged in capsules containing 4 or 10 granules)

Sites will be provided with study drug to administer for single dose Part 1 PK/PD to all eligible patients at that site. LCZ696 granules can be ingested after removing from the capsule. The liquid formulation can be compounded at the site / pharmacy [Pharmacy Manual].

Patients will be instructed to not use an ACEI for 36 hours after taking the single dose of LCZ696 to minimize the potential risk of angioedema due to overlapping ACEI-NEP inhibition. Patients should not use an ARB or renin inhibitor on the day of the single dose PK assessment visit.

At the completion of the single dose PK assessment visit (Visit 101 and/or 201), patients will be provided with open-label enalapril or will be instructed to resume their usual care as deemed necessary by the Investigator. The open-label enalapril will be obtained from a local commercial source by the site and provided to the patient. If needed, based on the patient's age and/or inability to swallow tablets, liquid enalapril may be used. The liquid enalapril is prepared at the site's pharmacy as per local regulations, and can be commercially sourced such as Epaned (if available). Patients receiving enalapril liquid formulation must return to the site for resupply at intervals dependent on the storage life of enalapril liquid formulation (every 1 month; or every 2 months if Epaned (enalapril) which has 2 month shelf life, is available and used).

# Part 2 (Efficacy) - Randomized treatment epoch

The LCZ696 study medication is available in three formulations: tablets, granules (mini-tablets) or liquid formulation (if patient cannot swallow granules) (refer to Table 5-1).

The enalapril study medication is available in two formulations: tablets or liquid formulation (refer to Table 5-2).

Patients will be randomized to initiate study medication at dose levels 1 or 2 for Groups 1 and 2, and 1x or 2x for Group 3, depending on whether they are ACEI/ARB naïve or depending on their ACEI/ARB dose prior to randomization (refer to Table 3-4, Table 3-5, Table 3-6). The study medication will be titrated at subsequent visits to the target dose. In addition to study medication, patients will continue to take optimal background HF therapy as considered appropriate by the Investigator and in accordance with standard HF treatment guidelines. The exception is that ACEI or ARB will be replaced by study drug. The use of open-label ACEI, ARB, or renin inhibitor in addition to randomized study drug is strictly prohibited.

The following study drugs will be provided for Part 2 (Efficacy):

- LCZ696 12.5mg (bottle will contain capsules, each capsule contains 4 granules of LCZ696 3.125mg)
- Placebo to match LCZ696 12.5mg (bottle will contain capsules, each capsule contains 4 granules of LCZ696 3.125mg matching placebo)
- LCZ696 31.25mg (bottle will contain capsules, each capsule contains 10 granules of LCZ696 3.125mg)
- Placebo to match LCZ696 31.25mg (bottle will contain capsules, each capsule contains 10 granules of LCZ696 3.125mg matching placebo)
- LCZ696 50mg tablets

- Placebo to match LCZ696 50mg tablets
- LCZ696 100mg tablets
- Placebo to match LCZ696 100mg tablets
- LCZ696 200mg tablets
- Placebo to match LCZ696 200mg tablets
- Enalapril 2.5mg tablets
- Placebo to match enalapril 2.5mg tablets
- Enalapril 5mg tablets
- Placebo to match enalapril 5mg tablets
- Enalapril 10mg tablets
- Placebo to match enalapril 10 mg tablets

All study medications will be supplied in bottles or blister cards. Capsules of LCZ696/matching placebo containing 4 granules or 10 granules per capsule will be provided for oral use. The granules can be swallowed (after the removal of the outer capsule) by the patient. LCZ696/matching placebo liquid formulation will be compounded by the site / pharmacy [Pharmacy Manual]. Patients taking < 8 granules (< 25 mg) for a dose will use the liquid formulation. The appropriate aliquot of liquid medication corresponding to the patient's dose will be given to the patient. Appropriate oral syringes will be provided to facilitate study drug administration as a liquid.

Sufficient medication will be provided for the treatment according to the study protocol (Table 5-1 and Table 5-2). Medication labels will be in the local language and comply with the legal requirements of the country. The labels will include storage conditions for the drug and the medication number, and will not include information about the patient.

Patients taking the liquid formulation of LCZ696/matching placebo or enalapril/matching placebo must return to the site every 4 weeks for resupply. The enalapril or enalapril placebo - liquid formulation will be prepared at the site / pharmacy based on the patient's age and ability to swallow adult tablets. The site personnel or the pharmacy at the sites is responsible for preparing enalapril liquid formulation (Pharmacy Manual). Given the burden of traveling to the site for study visits for patients and families, the parent/caregiver can come to the site without the patient for dispensation of study drug. Delivery of study drug to the patient can also be used where possible and allowed per local regulations.

Instructions for preparation of the liquid study drugs are provided in the Pharmacy Manual.

Table 5-1 LCZ696 drug supply for Part 1 (PK/PD) and Part 2 (Efficacy)

Study drug – Part 1 PK/PD open-label	Strength	Formulation
LCZ696	3.125 mg	Granules packaged in capsules of 4 or 10 granules in bottle
Study drug – Part 2 Efficacy double blind	Strength	Formulation
LCZ696 or matching placebo	3.125 mg	Granules packaged in capsules of 4 or 10 granules in bottle

Study drug – Part 1 PK/PD open-label	Strength	Formulation
LCZ696 or matching placebo	50 mg	Tablets in bottle
LCZ696 or matching placebo	100 mg	Tablets in bottle
LCZ696 or matching placebo	200 mg	Tablets in bottle

Table 5-2 **Enalapril drug supply for Part 2 (Efficacy)** 

Study drug – Part 2 Efficacy double blind	Strength	Formulation
Enalapril or matching placebo	2.5 mg	Tablets in bottle/blister
Enalapril or matching placebo	5 mg	Tablets in blister
Enalapril or matching placebo	10 mg	Tablets in blister

#### Part 1:

The LCZ696 study medication is available as granules or liquid formulation based on age, dosing, and patient's ability to take study medication (Pharmacy Manual).

#### Part 2:

The LCZ696 study medication is available in three formulations: tablets, granules (mini-tablets) or liquid formulation (refer to Pharmacy Manual) (if patient cannot swallow granules) (refer to Table 5-1).

The enalapril study medication is available in two formulations: tablets or liquid formulation.

All pediatric formulations of study medication (LCZ696 granules or liquid, enalapril liquid) will be made available to all age groups. The adult tablet formulations of LCZ696 and enalapril will be available to patients based on the patient's dosing and ability to swallow adult tablets (refer to Pharmacy manual).

Dispensing of medication to the subjects will be controlled by an Interactive Response Technology (IRT) system.

#### 5.1.2 Additional treatment

No additional treatment beyond investigational drug (LCZ696) and active comparator drug (enalapril) are included in this trial.

#### 5.2 Treatment arms

Part 1 (PK/PD): All patients will receive open-label LCZ696. Patients completing Part 1 and who are willing to participate in Part 2 will be provided open-label enalapril (or their standard of care HF regimen) by the study site.

Part 2 (Efficacy): Patients are assigned to one of the following two double blind treatment arms in a ratio of 1:1 at the randomization Visit 401:

- LCZ696
- Enalapril

# 5.3 Treatment assignment and randomization

At Visit 401, all eligible patients will be randomized via Interactive Response Technology (IRT) to one of the treatment arms. Patients will be stratified by age group (Age Groups 1, 2 and 3) and NYHA/Ross class group (Class I/II, Class III/IV) at randomization to ensure a balanced distribution of treatment allocation within each age strata. The Investigator or his/her delegate will contact the IRT after confirming that the patient fulfills all the inclusion/exclusion criteria. The IRT will assign a randomization number to the patient, which will be used to link the patient to a treatment arm and will specify a unique medication number for the first package of study drug to be dispensed to the patient. The randomization number will not be communicated to the caller.

The randomization numbers will be generated using the following procedure to ensure that treatment assignment is unbiased and concealed from patients/subjects and Investigator staff. A patient randomization list will be produced by the IRT provider using a validated system that automates the random assignment of patient numbers to randomization numbers. These randomization numbers are linked to the different treatment arms, which in turn are linked to medication numbers. A separate medication list will be produced by or under the responsibility of Novartis Drug Supply Management using a validated system that automates the random assignment of medication numbers to packs containing the investigational drug(s).

The randomization scheme for patients will be reviewed and approved by a member of the Randomization Group.

# 5.4 Treatment blinding

Part 1 (PK/PD) involves open-label LCZ696.

Part 2 (Efficacy) is a randomized, double-blind, active controlled study. Patients, Investigator and staff, persons performing the assessments, and data analysts will remain blind to the identity of the treatment from the time of randomization until database lock using the following methods:

- Randomization data are kept strictly confidential until the time of unblinding, and will not be accessible by anyone involved in the study with the following exceptions:
- 1. The independent and unblinded statistician, programmer and data personnel who are involved in preparing safety and efficacy interim analysis reports for the DMC. These personnel will not be involved in any other trial conduct related activities
- 2. The DMC members
- 3. An unblinded team, which is not involved in the conduct of the study, will evaluate the steady-state sparse PK blood samples collected from approximately 24 patients (approximately half of whom are expected to be randomized to LCZ696) in Part 2 Group 2 (Section 9.5.1).

4.

• A double-dummy design is used because the identity of the investigational treatment cannot be disguised, as the drug products are visibly different

• The identity of the treatments will be concealed by the use of investigational treatment that are all identical in packaging, labeling, schedule of administration, appearance, taste and odor

Unblinding will only occur in the case of patient emergencies (Section 5.5.9), at the time of interim analyses (Section 9.6), and at the conclusion of the study.

The randomization codes associated with patients/subjects from whom Part 2 PK samples are taken will be disclosed to PK analysts who will keep Part 2 PK results confidential until data base lock.

An assessment will be done by the appropriate site personnel and the Medical Lead (or designee) for any patient whose treatment code has been broken inadvertently or for any nonemergency reason to assess whether or not study treatment/investigational treatment should be discontinued and, if applicable, whether the patient can continue in the trial.

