#### 5.6.2 Discontinuation of study treatment

Patients may voluntarily discontinue study treatment for any reason at any time.

The emergence of the following circumstances will require permanent study drug discontinuation:

- Withdrawal of informed consent
- Investigator believes that continuation would be detrimental to the patient's well-being
- Suspected occurrence of angioedema; a patient with any signs or symptoms of clinically significant angioedema should be thoroughly evaluated by the Investigator

The emergence of the following circumstances will require temporary or permanent discontinuation (study drug may be restarted once these circumstances no longer exist):

- Use of an open-label ACEI, ARB or renin inhibitor
- Pregnancy and post-pregnancy during lactation period (Section 7.7)

Study drug may be discontinued at the Investigator's discretion if any of the following occurs:

- Any severe or suspected drug-related AE
- Any other protocol deviation that results in a significant risk to the patient's safety

The appropriate personnel from the site and Novartis will assess whether study drug should be discontinued for any patient whose treatment code has been broken inadvertently for any reason.

If permanent discontinuation of study treatment occurs and the patient/parents/guardians have not withdrawn consent, the patient should NOT be considered withdrawn from the study. The patient should return to the clinic as soon as possible, after discontinuation of study drug, for a study treatment discontinuation visit. Treatment discontinuation visit assessments detailed in the "unscheduled treatment discontinuation visit" (UNS) in Table 6-1 and Table 6-2 should be completed and recorded in the CRF. The Investigator must determine the primary reason for the patient's premature discontinuation of study treatment and record this information on the Dosage Administration CRF.

After study treatment discontinuation, the following minimum data should to be collected at clinic visits or via telephone visits:

new / concomitant treatments

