#### adverse events/serious adverse events

If the patient cannot or is unwilling to attend any visit(s), the site staff should maintain regular telephone contact with the patient, caregiver/parent, or with a person pre-designated by the patient. This telephone contact should preferably be done according to the study visit schedule.

The Investigator must also contact the IRT to register the patient's discontinuation from study treatment.

If study drug discontinuation occurs because treatment code has been broken, please refer to Section 5.5.9.

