### 9.1 Analysis sets

For Part 1: All subjects with at least one dose of study drug will be included in safety analysis set. All subjects with evaluable PK/PD data will be included in the PK/PD data analysis.

For Part 2 (Efficacy), the following populations will be used for the statistical analyses

The full analysis set (FAS) will consist of all randomized patients with the exception for those patients who have not been qualified for randomization and have not received study drug, but have been inadvertently randomized into the study. Following the intent-to-treat principle, patients will be analyzed according to the treatment to which they were assigned at randomization. Efficacy variables will be analyzed based on the FAS as the primary population.

The Safety Population (SAF) will consist of all patients who received at least one dose of study drug and have at least one post-baseline safety assessment. Of note, the statement that a patient had no AEs also constitutes a safety assessment. Patients will be analyzed according to the treatment actually received. The safety population will be used for the analyses of safety variables.

The Per-Protocol (PP) population will be a subset of the FAS which will consist of the patients who do not have major deviations from the protocol procedures in the double-blind study stage. Major protocol deviations will be pre-specified prior to unblinding treatment codes for analyses. This supplemental efficacy population will be used to support the primary analysis results.

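### After an inadvertent or non-emergency code break, Section 5.4 lets site and sponsor staff decide whether a child stays in the trial, while Section 5.6.2 confines the same assessment to study drug

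*Protocol*

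**What the plan says.** Section 5.4 provides for an assessment by site personnel and the Medical Lead or a designee "for any patient whose treatment code has been broken inadvertently or for any nonemergency reason". It has two parts: whether treatment should be "discontinued and, if applicable, whether the patient can continue in the trial". No criteria are given for the second part, and nothing says that outcome follow-up continues whatever is decided.

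Section 5.6.2 takes up the same kind of event. Staff from the site and the sponsor "will assess whether study drug should be discontinued for any patient whose treatment code has been broken inadvertently for any reason". Trial participation is not mentioned. The section then sets a general rule: if drug is stopped permanently and consent stands, "the patient should NOT be considered withdrawn from the study". At its end it adds: "If study drug discontinuation occurs because treatment code has been broken, please refer to Section 5.5.9". Section 5.5.9 explains how to break a code in an emergency and has no rule on follow-up.

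Section 5.5.5 and Section 6 likewise keep children who stop study drug in the study with their scheduled assessments. Neither makes an exception for code breaks. In Section 9.1 the full analysis set follows intent to treat: "patients will be analyzed according to the treatment to which they were assigned at randomization". The SAP supplied covers regional subpopulations, takes its analysis sets from a main SAP that is not among the documents, and does not mention code breaks.

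**The concern.** Two passages on one event give different powers. Under 5.6.2 the only question after the break is whether drug stops. Under 5.4 there is a second question, whether the child stays in the trial, and it is decided after randomisation by people who may know the arm and the clinical course.

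Nothing in the analysis calls for such a removal. Section 27.2 says that the primary analysis includes data collected after treatment discontinuation. The only exception is for patients affected by the urgent safety measure, and that exception has its own justification. A child whose code has been broken therefore remains informative to Week 52. If follow-up ends early, the child stays in the full analysis set and is ranked under Section 9.4.3 on what is available, with NYHA/Ross and PGIS carried forward. Categories 1 and 2 sit at the bottom of the ranking and depend on events being observed through Week 52. Removal that depends on arm or prognosis could therefore shift the comparison in either direction.

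**Working it through.** **1. The passages side by side**

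| Place | Trigger | What is decided or required |
|---|---|---|
| 5.4 | Code broken inadvertently or for a non-emergency reason | Study treatment and, if applicable, continuation in the trial |
| 5.6.2, code-break sentence | Code broken inadvertently | Study drug only |
| 5.6.2, general rule | Drug stopped permanently, consent not withdrawn | Not withdrawn from the study |
| 5.5.5 | Drug stopped temporarily or permanently | Visits continue to the end of the study |
| Section 6 | Drug stopped early | Remains in the study, Table 6-2 assessments |
| 5.5.9 (target of the 5.6.2 cross-reference) | Emergency code break | How to break the code; nothing on follow-up |

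The second part of the 5.4 decision cannot mean staying on drug, because the same sentence has already dealt with drug. The glossary also separates treatment discontinuation from withdrawal of consent. No passage resolves the difference.

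**2. Who may know the arm.** For an emergency break, 5.5.9 says the investigator receives the treatment identity, while the monitor and study team are told only that the code was broken. For an inadvertent break the documents do not say who learns what. Knowledge of the arm is therefore possible, most plainly at the site, but not certain for every decider.

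**3. What could be lost.** Section 6 gives anyone leaving the study early, for any reason, a visit with all final-visit assessments. In Table 6-2 these include NYHA/Ross, PGIS and PedsQL. Section 6 also asks for survival status at 52 weeks when a family withdraws, refuses or cannot return. What remains unobserved is worsening HF after exit, non-fatal Category 1 events after exit, and NYHA/Ross and PGIS at Week 52 itself.

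**4. Illustration only.** No document gives the number of code breaks, so the following shows sensitivity and is not an estimate. Inputs are Table 9-2 (Categories 1 to 5: LCZ696 9, 15, 8.1, 10.0, 57.9%; enalapril 13, 19, 12.2, 11.3, 44.5%), n = 180 per arm and two-sided alpha 0.05. The test is the five-category Wilcoxon test.

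Win probability w = sum over categories of p(LCZ696) × [p(enalapril in a worse category) + ½ p(enalapril in the same category)]
= 0.09×0.065 + 0.15×0.225 + 0.081×0.381 + 0.10×0.4985 + 0.579×0.7775 = 0.5705.

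The odds (1 − w)/w = 0.4295/0.5705 = 0.753 reproduce the figure in Section 9.7.

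Null variance with tie correction, N = 360 and pooled proportions 0.11, 0.17, 0.1015, 0.1065, 0.512: V ≈ (N+1)/(12n²) × (1 − Σp³) = 361/388,800 × (1 − 0.1427) = 0.000796, so SE = 0.0282. Power = Φ(0.0705/0.0282 − 1.96) = Φ(0.54) ≈ 70.5%. At 177 per arm the same formula gives about 70%, as Section 9.7 states.

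Moving one enalapril child from Category 2 to Category 4 lowers w by (0.835 − 0.629)/180 = 0.00114. Moving one LCZ696 child the same way raises it by (0.4985 − 0.225)/180 = 0.00152. With the variance recomputed each time:

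| Assumption about removed children | w | Power |
|---|---|---|
| None removed | 0.5705 | 70.5% |
| 4 enalapril, Category 2 recorded as unchanged | 0.5659 | 64.6% |
| 4 LCZ696, Category 2 recorded as unchanged | 0.5766 | 77.4% |
| 4 enalapril, Category 2 recorded as worsened | 0.5679 | 67.2% |
| 4 LCZ696, Category 2 recorded as worsened | 0.5740 | 74.5% |
| 4 enalapril irrespective of prognosis (19% of them Category 2, recorded as unchanged) | 0.5696 | 69.4% |
| 2 per arm, Category 2 recorded as unchanged | 0.5712 | 71.4% |

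**The case against.** **Scope.** A reader might infer that any broken code exposes a child to removal. The text does not support that. The 5.4 clause covers inadvertent and non-emergency breaks, and the same section confines planned unblinding to patient emergencies, interim analyses and the end of the study. Emergency breaks under 5.5.9 are outside it. This stands, and the point is limited accordingly.

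**Degree of contradiction.** Section 5.6.2 has no sentence of its own saying that unblinded children are followed. It reaches them through the general rule on stopping drug. Section 5.4 says only "if applicable" in substance, does not state that data collection ends, and could be read as subject to 5.5.5, 5.6.2 and Section 6. That reading is possible, but 5.4 does not say so and refers to none of them. Its separate decision on trial continuation has no function if follow-up always continues.

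**Loss of data.** A reader might infer that all later outcomes of a removed child disappear. The exit visit means that the carried-forward value would normally be a fresh assessment, and deaths to Week 52 are sought. Section 9.4.3 also classifies on all retrievable information. This stands and narrows the loss to the items in step 3 of the working. The survival check is written for families who withdraw, refuse or cannot return, so its use after a removal under 5.4 is reasonable but not stated.

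**Size.** The extreme rows of the table put every removal in one arm, make every removed child a future Category 2 case and record each as unchanged. The test is the supportive one in Section 9.4.5, not the primary ranked analysis. This stands.

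**Timing.** At Amendment 7, recruitment was closed and 339 of 375 treated patients had completed or discontinued. Of the 36 still ongoing, 31 were on drug. Rewording now protects few children, and Section 27.2 already asks for every effort to keep patients to Week 52. This stands, and it is why the fix includes reporting as well as rewording.

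**Conclusion.** The inconsistency is real and the 5.4 clause is wrong as written. For inadvertent or non-emergency code breaks it opens a route by which a randomised child with valid consent can leave follow-up through a decision of people who may know the arm. Sections 5.5.5, 5.6.2 and 6 provide the opposite when drug is stopped.

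The size of any bias cannot be determined, because the number of code breaks and of removals is not given. A reader might infer that power falls to about 65% or rises to about 77%. Those figures are a one-arm worst case with four removals on the supportive test. With balanced removals, or removals unrelated to prognosis, the shift is about one percentage point. Nor do the documents show that any child was in fact removed under the clause. The conclusion rests on the text of the protocol supplied; the main SAP was not available.

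**What to change.** 1. In Section 5.4, strike everything after the first word of "discontinued and, if applicable, whether the patient can continue in the trial", so that the assessment concerns study treatment only. Then add: *Whatever is decided about study treatment, the patient stays in the study and is followed to Week 52 as in Section 5.6.2, unless consent is withdrawn.*
2. At the end of Section 5.6.2, point the cross-reference for drug stopped because of a code break to that rule in place of 5.5.9.
3. In the study report, list by arm every child whose participation ended under the 5.4 clause, with the date, who knew the arm, and the last outcome information available. If there are none, say so.

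The cost is one deletion, one sentence, one corrected cross-reference and a short listing. No visits are added, because the protocol already schedules this follow-up. The change concerns outcome follow-up only and leaves the decision on study drug where it is.
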